4.1. Overall Study Design and Plan

Study NGAM-13 is designed as a prospective, multicenter, randomized, double-blind, parallel group, placebo-controlled, phase 3 superiority study, with an additional double-blind, crossover safety and efficacy follow-up phase.

In the first phase of the study, from enrolment to Week 9, patients will receive Panzyga or placebo administered 3 times within 9 weeks in 3-week intervals, according to their randomized treatment sequence. After Week 9 all patients will be switched to the alternative for another 3 treatments in the crossover phase of the study. Dosing and dosing intervals will be the same for all study drug administrations in both study phases, namely Panzyga 2 g/kg bodyweight (BW), administered as 1 g/kg BW daily for two consecutive days) or placebo (0.9% w/v sodium chloride infusion equivalent in volume to 1 g/kg BW Panzyga daily for two consecutive days).

Up to █ sites (USA and rest of the world) are projected to participate.

After the first █ patients have been enrolled, the study enrollment will be put on hold until the Independent Data Monitoring Committee (IDMC) has reviewed unblinded safety and PK data of these █ patients and given the green light to pursue the study.

The duration of the initial parallel-group phase will be 9 weeks, plus up to 28 days from screening to randomization, the duration of 2nd phase after the crossover will also be 9 weeks. After the initial phase patients will directly continue with the second phase without any wash-out time.

Patients eligible after screening will be randomized in a balanced 1:1 ratio to one of two treatment sequences:

- (Panzyga – Placebo): 3 administration cycles with Panzyga, followed by 3 administration cycles with placebo
- (Placebo – Panzyga): 3 administration cycles with placebo, followed by 3 administration cycles with Panzyga

The study population will be prospectively balanced according to the stratification factors specified in section 3.2.4 above. Psychological and behavioral evaluations, in particular the CY-BOCS, will be conducted at every visit, i.e. every 3 weeks during the initial parallel-group phase and at Week 18 / Final Visit; please refer to the protocol for the complete flow chart of assessments.

It is important to keep in mind that the primary efficacy evaluation of this study will be based on changes in the total CY-BOCS score from Baseline to Week 9, no data collected in the cross-over phase will be considered. Patients dropping out after Week 9 are not considered as withdrawals for the primary objective of the study.

As the first secondary endpoint is to assess the durability of the clinical benefit, this analysis will be based on data collected throughout the whole study on patients receiving Panzyga in the initial, parallel-group phase (baseline to Week 9) of the study, i.e. on patients randomized to treatment sequence Panzyga – Placebo.

Analyses of all subsequent secondary endpoints will be based on data collected during the parallel-group phase of the study only, i.e. up to Week 9.

After █ patients have completed blinded treatment (Visit Week 9), an interim review of the preliminary safety and efficacy data will be conducted by Independent Data Monitoring Committee (IDMC). At this timepoint, the IDMC will independently evaluate all data accrued in this pivotal study to provide a statement on whether emerging data confirm the prospect of direct benefit and positive risk-benefit ratio for PANS patients treated with Panzyga. IDMC confirmation will justify the submission to concerned Health Authorities of additional study protocol(s) evaluating other dose regimens of Panzyga treatment in patients with PANS. The actual numeric results will not be shared with the Sponsor or Investigators to ensure that bias will not affect subsequent study decisions since the data of the first █ patients will be included in the final statistical analysis.

An interim analysis will be performed by an independent statistician after █ patients have completed the initial 9-week treatment period, to verify the initial assumptions, and to allow for the following adaptations in study design:

1. Adaptive enrichment in the study population

The CY-BOCS scores at Visit 9 will be analyzed with respect to the following covariates/sub-groups in order to identify those that exhibit a promising treatment effect. It will then be determined whether future enrollment will be restricted to any (or a combination) of these:

██████████	██████████	██████████
██████████	██████████	██████████
██████████	██████████	██████████
██████████	██████████	██████████
██████████	██████████	██████████

2. Sample size re-estimation to achieve the desired power of 80% while maintaining the overall type 1 error rate of 2.5%. Please refer to section 6 for details on the sample size determination.

Study enrollment will continue while enough patient data is accrued to conduct the interim analysis. In case the sample size re-assessment does not result in a required total of more than the number of patients already enrolled at the time, enrollment will be stopped but patients already randomized will continue in the study until the planned end, i.e. for 18 weeks.

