##### 3.1.2 Secondary Endpoint

- To assess behavioral changes by means of the following standardized assessments:
  - CY-BOCS score at the end of the follow-up period at Week 18 will be compared to the Week 9 scores within the (Panzyga – Placebo) treatment sequence group to assess the durability of the clinical benefit associated with Panzyga treatment
  - Clinical Global Impression (CGI)
  - Parent & Child OC Impact Scale – Revised (COIS-RP and COIS-RC)
  - SNAP-IV 26 item Scale
  - Parent Tic Questionnaire (PTQ)

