#### **4.2.2 Forbidden Concomitant Therapy**

Administration of forbidden concomitant therapy as listed below does not automatically trigger patient withdrawal; the patient will be moved from the per protocol analysis set to the intent-to-treat set (see Section 9.2.1). The following medications or therapies are not permitted during participation in this study:

- Immunosuppressive agents
- Antibiotics (unless given per protocol Section 4.2.1);
- CBT (unless applied per protocol Section 4.2.1);
- SSRIs (unless given as allowed per protocol Section 4.2.1);
- Mood stabilizers (e.g. Depakote, Lamotrigine, Lithium)
- Psychotropic medication for OCD, anxiety or tic disorder (e.g. alpha-2 agonists or antipsychotics), unless given in single doses prior to blood draws or infusions and after completion of psychiatric evaluations when dealing with agitated patients (e.g. one-time doses of Lorazepam);
- Stimulants for ADHD (unless given per protocol Section 4.2.1);
- THC-containing agents;
- CBD/CBM-containing agents without THC (unless applied given per protocol Section 4.2.1);
- NSAIDs (unless given per protocol Section 4.2.1);

- Immunoglobulin treatment other than Panzyga. Patients will be withdrawn from study treatment if IgG preparations other than Panzyga are administered;
- Other blood or plasma-derived products;
- Plasma exchange procedures, plasmapheresis;
- Known nephrotoxic medication;
- Live attenuated vaccines such as measles, rubella, mumps and varicella;
- Any experimental drug;
- Melatonin.

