### 4.3.2 Premature Patient Withdrawal from Study Treatment

Patients may be withdrawn from study treatment for the following reasons:

- Occurrence of a condition or disease that interferes with the study treatment or represents an exclusion criterion.
- Administration of IVIG other than Panzyga. All patients who received at least one dose of the study treatment should be followed up per protocol until the study end without administration of the study product.

- Occurrence of an AE or SAE, which in the opinion of the investigator, precludes further treatment with study medication (Section 7.3.2).

If a patient shows worsening of their symptoms based on CGI-Improvement ratings, they will be presented to the site PI for review and treatment planning. Patients for whom worsening continues at a minimal level ("5" or "mildly worse") for an extended period of six weeks (2 visits) or moderately or greater level ("6" or "7"; much worse or very much worse) since last visit (up to three weeks) will be considered for premature withdrawal from the study drug and administration of appropriate standard of care treatment unless clinical interventions using approved study procedures and/or mediations have a reasonable likelihood to improve symptoms. Patients who experience an emergency worsening of symptoms may at the discretion of the site clinician be withdrawn from the study drug at any time to obtain necessary standard of care treatment. In addition, patients who develop exclusionary criteria (e.g. bipolar disorder, suicide attempt) will be withdrawn from the study drug and will receive appropriate standard of care treatment. All patients withdrawn from the study drug prematurely will be asked to continue the study as planned with modification of the study schedule (e.g. IMP administration and related to it safety lab tests will be omitted). Details of concomitant medications and procedures administrated per standard of care will be captured in patient case reports.

The eCRF will contain an End of Treatment and an End of Study page. The End of Treatment page will record whether the patient will be followed up per protocol, to allow for correct patient status tracking and to provide the reason for the drug withdrawal.

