## 7.2.2 Assessments for Secondary Efficacy Endpoint(s)

To assess behavioral changes, durability of improvement of neuropsychiatric symptomatology and behavior in PANS patients will be determined with the clinician-rated CY-BOCS score. The mean change in total CY-BOCS score from Week 9 to Week 18 within the (Panzyga – Placebo)

treatment sequence group will be assessed to demonstrate that no statistically significant increase occurred in this period.

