3.2.2. Secondary Target Variables

Efficacy:

CY-BOCS score at the end of the follow-up period at Week 18 will be compared to the Week 9 scores within the (Panzyga – Placebo) treatment group to assess the durability of the clinical benefit associated with Panzyga treatment.

The protocol specifies the following standardized instruments for the assessment of behavioral changes as secondary efficacy endpoints:

- Clinical Global Impression (CGI) – For the confirmatory endpoint analysis the CGI-I (CGI – Improvement) total score will be used
- Parent & Child OC Impact Scale – Revised (COIS-RP and COIS-RC) – For the confirmatory endpoint analysis the COIS-RP total score will be used
- The Swanson, Nolan, and Pelham Rating Scale (SNAP-IV, 26 item)
- Parent Tic Questionnaire (PTQ)

These scores are therefore considered as secondary target variables; please refer to the protocol for details on these instruments.

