All protocol deviations documented during the conduct of the study or identified at the data review process prior to DB lock will be reviewed and classified as minor or major, and with respect to their importance for the planned analyses. This classification of protocol deviations is the joint responsibility of the clinical study manager, the study statistician, and Octapharma's responsible medical expert, and will be agreed and documented before the database is locked or unblinded.

For this study no separate safety population is defined as the FAS coincides with all patients who received at least part of one infusion of Panzyga or placebo. All safety data will thus be analyzed using the FAS. In the event that a patient takes the wrong study drug (i.e., did not take the randomized study drug), the actual treatment received will be used for safety analyses.

All efficacy analyses will primarily be based on the ITT population. In addition, analyses of the primary and secondary endpoints will be repeated on basis of the FAS, unless FAS and ITT coincide. All efficacy analyses will follow the intent-to-treat principle, i.e. patients will be analyzed according to the group they were originally assigned, regardless of what treatment they actually received.

Selected efficacy analyses, but at least the primary and secondary efficacy analyses, will be repeated for the PP population.

Screening failures will only be accounted for in the overall patient disposition, and individual data will be listed.

The assignment of each patient into the respective analysis populations will be determined before the statistical analysis in a data review meeting by a panel consisting of a medical expert from the sponsor, the clinical project manager, the data manager and the study statistician.

8. General Issues for Statistical Analysis

The primary target variable in this study is the CY-BOCS, the mean changes in the total CY-BOCS from Baseline to Week 9 will be compared between Panzyga and Placebo by a confirmatory statistical test to demonstrate superiority.

Descriptive summaries will be presented for each of the primary, secondary, and exploratory variables. In general, summaries will be presented by treatment group in a side-by-side fashion, using a set of standard summary statistics according to the different types of data:

Binary data (whether or not an event has occurred): counts and proportions

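### No readable rule handles CY-BOCS scores taken after rescue therapy between Week 9 and Week 18, so the durability analysis can mask relapse

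*SAP*

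**What the plan says.** **Endpoint.** SAP 3.2.2 states "CY-BOCS score at the end of the follow-up period at Week 18 will be compared to the Week 9 scores", and Protocol 3.1.2 places the comparison "within the (Panzyga – Placebo) treatment sequence group to assess the durability of the clinical benefit". There is no concurrent control. SAP 4.1 adds that "this analysis will be based on data collected throughout the whole study on patients receiving Panzyga in the initial, parallel-group phase".

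**Criterion.** Protocol 7.2.2 says the mean change in the "treatment sequence group will be assessed to demonstrate that no statistically significant increase occurred in this period". The readable text gives no margin.

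**What happens to a worsening child.** Under Protocol 4.3.2, children who meet the CGI-I worsening rules "will be considered for premature withdrawal from the study drug and administration of appropriate standard of care treatment", and "All patients withdrawn from the study drug prematurely will be asked to continue the study as planned with modification of the study schedule". Protocol 3.3.1 reads differently: on clinically important deterioration the child leaves the study after termination procedures.

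**Analysis rules.** SAP 7: "All efficacy analyses will follow the intent-to-treat principle, i.e. patients will be analyzed according to the group they were originally assigned", whatever treatment was actually received. SAP 8.2 keeps withdrawals in every presentation to which they contribute data. SAP 8.3 does not impute missing secondary variables. SAP 7 repeats the secondary analyses in the FAS and in the per-protocol set. Under Protocol 4.2.2, after forbidden therapy "the patient will be moved from the per protocol analysis set to the intent-to-treat set".

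**The concern.** The first secondary objective is to verify that the symptom reduction is sustained in children treated with Panzyga. A child who loses benefit on saline after Week 9 and needs other therapy is evidence against that. The Week 18 score of such a child may reflect the other therapy more than any lasting effect of Panzyga. The comparison has no control arm, so this cannot cancel between groups. The criterion is the absence of a significant rise, so anything that lowers Week 18 scores, or removes high ones, moves the result toward the desired conclusion.

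The problem lies in the estimate itself. It would remain even if the test were replaced by a confidence interval against a margin.

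**Working it through.** The plan has no figure to reproduce. The sample size, effect size and SD are redacted, and no power for the durability test is readable. The check is therefore a trace through the rules, followed by illustrative arithmetic.

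**Step 1: follow one child through the readable rules.** A child in the Panzyga–Placebo sequence worsens after Week 9.
- Under Protocol 4.3.2 the child may start standard of care and is still seen at Week 18. SAP 7 and 8.2 put that score into the ITT mean. The FAS repeat keeps it too, because the child has been infused.
- If the child leaves and has no Week 18 score, SAP 8.3 leaves the value missing and the child drops out of the change from Week 9.
- If the child is excluded from the per-protocol set, the effect there is the same as a missing score.

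**Step 2: mean rise hidden by post-rescue scores.** Assumptions, none from the documents: a relapse is 10 points, and a stated share of rescued children is restored to the Week 9 level.

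Hidden rise = share rescued × share restored × 10

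| Share of sequence rescued | 50% restored | 100% restored |
|---|---|---|
| 10% | 0.1 × 0.5 × 10 = 0.5 | 0.1 × 1 × 10 = 1 |
| 20% | 0.2 × 0.5 × 10 = 1.0 | 0.2 × 1 × 10 = 2 |
| 30% | 0.3 × 0.5 × 10 = 1.5 | 0.3 × 1 × 10 = 3 |

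**Step 3: mean rise left when relapsers are missing or excluded.** Let r be the share relapsing, q the share of relapsers without a usable score, and 0 the mean change in all other children.

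Observed mean rise = 10 × r(1 − q) / (1 − rq)

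With r = 0.3 the full rise is 10 × 0.3 = 3.0 points. At q = 0.5 the observed rise is 10 × 0.15 / 0.85 = 1.8. At q = 0.8 it is 10 × 0.06 / 0.76 = 0.8. Dropping relapsers therefore masks in the same direction as rescoring them.

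**Step 4: effect on the test.** A one-sample t-test on the Week 9 to Week 18 change was simulated at one-sided 2.5%, with 20,000 runs per setting. The assumptions are an SD of change of 6, a 10-point mean relapse and 20, 30 or 45 children in the sequence. The table gives the chance of a significant rise when 30% relapse.

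| n | No relapser restored | 50% restored | 80% restored |
|---|---|---|---|
| 20 | 0.38 | 0.13 | 0.05 |
| 30 | 0.55 | 0.19 | 0.06 |
| 45 | 0.75 | 0.28 | 0.08 |

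The mean rise in these three columns is about 3.0, 1.5 and 0.6 points. Over 20–40% relapse and all three sizes, the chance runs 0.21–0.93, 0.09–0.44 and 0.04–0.11 respectively.

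**The case against.** **Redaction.** SAP 10.2, where this analysis would be specified, is blacked out, and Protocol 9.2.1, 9.2.2 and 9.2.4 cannot be read. A reader might infer that the plan uses Week 18 scores as observed. No readable sentence says so. The inference comes from the general rules in SAP 4.1, 7, 8.2 and 8.3, and a specific rule in 10.2 could override them. This stands, and the point is conditional on it.

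**Discontinuation.** Under Protocol 3.3.1 the deteriorating child leaves the study, so no post-rescue score would exist. The Early Termination Visit has the Week 18 procedures (Protocol 4.3.1), and SAP 4.1 places CY-BOCS at Week 18 or the final visit, so the relapse could be captured before rescue. That would remove the bias for those children. However, Protocol 4.3.2 says the opposite, and no readable text makes an Early Termination score the Week 18 value. Without that, Step 3 applies.

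**Per-protocol set.** A reader might infer that this repeat certainly drops the relapsers. SAP 7 excludes deviations that may affect the primary outcome, which ends at Week 9, so therapy started later need not count. Against that, the SAP 7 list includes prohibited medication and withdrawal criteria that develop during the study, and Protocol 4.2.2 also points to exclusion. Exclusion is likely but not certain.

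**Nature of the endpoint.** A reader might say that rescued relapses are counted as sustained benefit. They are not: the endpoint is a mean change, and a rescued child dilutes a rise.

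**Unscored relapse.** SAP 4.1 could be read to mean that CY-BOCS is not taken between Weeks 9 and 18. It defers to flow charts that are redacted, and Protocol 3.2 refers to efficacy assessments with each cycle. This cannot be settled.

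**Size.** Full restoration is the upper extreme. With visits at Weeks 9, 12, 15 and 18, the milder worsening rule needs six weeks and the stronger rule up to three. Outside emergencies, rescue would therefore start at about Week 15 or Week 12, leaving three to six weeks to recover. Partial restoration is plausible, which is why the range starts at 50%.

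**Conclusion.** The concern holds in a limited form. On the readable rules, a Week 18 CY-BOCS obtained after standard-of-care or prohibited PANS therapy enters the durability mean, and a missing score is dropped. Both favour a finding of durability, and the per-protocol repeat cannot be relied on to correct it.

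The size is unknown because the documents give no rescue rate. Under the assumed 10-point relapse, 10–30% rescued hides 0.5–1.5 points at 50% restoration and 1–3 points at full restoration. The direction does not depend on those values, provided rescue improves scores or missing scores come mainly from relapsers.

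The documents do not support saying that the plan prescribes as-observed scores, that it counts rescued children as successes, or that every repeat analysis is certainly biased. The primary result is untouched, since SAP 4.1 uses no crossover-phase data for it.

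**What to change.** Unless SAP 10.2 already does so, prespecify for the durability endpoint an analysis in which starting standard-of-care or prohibited PANS therapy (including non-study IgG) between Week 9 and Week 18 counts as loss of benefit. Two workable forms:

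- The proportion of the sequence that keeps its Week 9 benefit at Week 18 without such therapy, with the threshold for keeping benefit fixed in advance.
- The mean change, using the worse of the observed Week 18 score and any CY-BOCS taken after Week 9 and before that therapy.

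The first form is safer if few CY-BOCS scores exist between those visits, because the last score before rescue may predate the relapse. Substituting Baseline imposes total loss of benefit, so it belongs only in a conservative sensitivity analysis.

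Also:
- Do not exclude these patients from the per-protocol repeat of this endpoint because of that therapy.
- Report the number and timing of rescued patients, and show the as-observed result alongside.
- State whether an Early Termination CY-BOCS counts as the Week 18 value.
- Reconcile Protocol 3.3.1 (discontinued from the study) with 4.3.2 (off study drug but followed).

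The cost is SAP wording, the reconciliation in the protocol, one flag derived from concomitant-therapy data already collected, and one more analysis. The durability estimate may become less favourable.

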**Number of Patients:**

It is estimated that a minimum of █ pediatric patients will need to be enrolled to ensure that █ patients are evaluable for the primary endpoint (considering a 10% dropout rate). The total number of patients enrolled for the final analysis may increase, depending on the outcome of the interim analysis.

Enrollment was staggered in the sense that it was paused after the first █ patients had been randomized and enrolled in the study, in order to enable a planned IDMC review of unblinded safety and PK data, including IgG trough levels. Enrollment resumed only after IDMC data review of the first █ patients had been completed, and the IDMC had recommended to continue enrollment in the study.

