**Test Product, Dose, and Mode of Administration:**

Panzyga is a 10% solution of IVIG ready for intravenous (IV) administration. The product is delivered as ready-to-use solution in glass bottles. Panzyga should be stored and transported light-protected at +2°C to +8°C (36°F to 46°F) and must not be frozen.

Patients are randomly assigned (1:1) to Panzyga or placebo as initial treatment arm. In the Panzyga arm, Panzyga will be administered in a dose of 1 g/kg body weight (BW) daily for two consecutive days, and if tolerated, administered in three-week intervals up to nine weeks

Name of Sponsor/Company: Octapharma Pharmazeutika Produktionsges.m.b.H.	
Name of Investigational Product: Panzyga	Protocol Identification Code: NGAM-13
Name of Active Ingredient: Immune Globulin Intravenous, Human 10%	Date of Final Protocol: 21 July 2023

(total Panzyga exposure 6 g/kg BW). After completion of the first phase of the study, blinded crossover assignment will be done: patients previously in the Panzyga arm will be assigned placebo and patients previously in the placebo arm will be assigned Panzyga, administered at the same regimen.

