## 4 STUDY POPULATION

### 4.1 Population Base

Patients will be aged 6–17 years, with moderate to severe symptoms PANS with prominent and stable OCD symptoms (i.e. CGI—Severity-OCD rating of  $\geq 4$  or higher on 2 ratings without a change of more than 1 unit between measurements). All patients will meet criteria for PANS, including the sudden onset of obsessive-compulsive symptoms and at least two of seven additional associated neuropsychiatric symptoms. It is estimated that a minimum of █ patients will need to be enrolled, to ensure that at least █ patients are evaluable for the primary endpoint. The total number of patients enrolled for the final analysis may change, depending on the outcome of the interim analysis. Patients who drop out or are withdrawn from the study will not be replaced, but enrollment will continue until the total evaluable number of required patients for primary endpoint assessment has been reached.

Enrollment was staggered in the sense that it was paused after the first █ patients had been randomized and enrolled in the study, in order to enable a planned IDMC review of unblinded safety and PK data, including IgG trough levels. Enrollment resumed only after IDMC data review of the first █ patients had been completed, and the IDMC had recommended to continue enrollment in the study.

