Because the available knowledge on the effect of intravenous immunoglobulin (IVIG) in the PANS population is limited, this study will deploy an adaptive enrichment design with an interim analysis after █ patients have completed the initial 9-week treatment period, at which time a decision will be made based on prespecified criteria whether to continue enrollment in the overall population (PANS) or to restrict future enrollment on a targeted subpopulation, including e.g. the subgroup of patients diagnosed with pediatric autoimmune neuropsychiatric disorders associated with streptococcal infection (PANDAS); please refer to section 5.1 for details on the interim analysis.

The possible design adaptations at the interim analysis will also include a sample size re-assessment on basis of the observed changes in CY-BOCS.

The structure and content of this SAP provides sufficient detail to meet the requirements identified by the FDA and International Conference on Harmonization (ICH) of Technical Requirements for Registration of Pharmaceuticals for Human Use: Guidance on Statistical Principles in Clinical Trials¹.

The following documents were reviewed in preparation of this SAP:

- Clinical Study Protocol NGAM-13, Version 3.0, dated 25-Jan-2021

¹ International Conference on Harmonization. (1998). Guidance on Statistical Principles. ICH Topic E9 (Statistical Principles for Clinical Trials), and its Addendum on Estimands and Sensitivity Analysis, E9(R1), 2019-11-20.

The reader of this SAP is encouraged to also read the clinical protocol for details on the planned conduct of this study. Operational aspects related to collection and timing of planned clinical assessments are not repeated in this SAP unless relevant for the specification of the planned analyses.

Property of Octapharma. Do not copy or distribute without written permission.

2. Purpose

This SAP outlines the statistical analyses to be performed on data collected in study NGAM-13, and the resulting output that will be compiled to support the completion of the CSR.

The planned analyses identified in this SAP will be included in regulatory submissions and/or future manuscripts. Exploratory analyses not necessarily identified in this SAP may be performed to support the clinical development program. Any post-hoc or unplanned analyses performed that are not identified in the final SAP will be clearly identified in the respective CSR.

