6.1. Patient Replacement Policy

There will be no patient replacement in this study, but enrollment will continue until it is foreseeable that the number of patients required (according to the possible adaptations and the revised sample size determined at the interim analysis) for the evaluation of the primary endpoint will be achieved with the currently enrolled patients. 'Foreseeable' in this context means that the required number of evaluable patients will be achieved if the drop-out rate at the time remains unchanged for the remainder of the study.

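### The enrolment-stop rule in SAP 4.1 counts enrolled patients, while SAP 6.1 and protocol 4.1 and 4.3.3 count evaluable patients; the two rules need to be made one

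*SAP*

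**What the plan says.** SAP 4.1 (item 2 of the interim adaptations) describes a re-estimation aimed at 80% power with an overall type 1 error rate of 2.5%. Enrolment stays open while the interim data accrue. It is then stopped if the re-assessment "does not result in a required total of more than the number of patients already enrolled at the time"; patients already randomized carry on to Week 18. The sentence does not mention evaluability, drop-out or membership of a retained subgroup.

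Other sections use a different count:

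- SAP 6.1, repeated in protocol 4.3.3, continues enrolment until the number needed for the primary endpoint, as revised by the interim adaptations, is foreseeable. Foreseeable means that "the required number of evaluable patients will be achieved if the drop-out rate at the time remains unchanged" to the end of the study.
- Protocol 4.1 says "enrollment will continue until the total evaluable number of required patients for primary endpoint assessment has been reached".
- The Study Outline sets an enrolled number above the evaluable number to allow for 10% drop-out (both numbers are redacted).

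On enrichment, the SAP Preface allows the interim decision to "restrict future enrollment on a targeted subpopulation". Only future enrolment is restricted.

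On direction, the Study Outline gives a minimum and adds: "The total number of patients enrolled for the final analysis may increase, depending on the outcome of the interim analysis". Protocol 4.1 says instead that the total may change.

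**The concern.** An enrolled patient is not necessarily an evaluable one. When the number enrolled equals the evaluable requirement, SAP 4.1 read literally says stop, while SAP 6.1, protocol 4.1 and protocol 4.3.3 say continue. The purpose of the re-estimation is to secure 80% power, so a rule that can stop short of the number just calculated works against it.

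Enrichment adds a second gap. Because enrolment continues during the interim, some children enrolled in that window may fall outside a subgroup chosen afterwards. Nothing in the SAP 4.1 sentence removes them from the count, although they may add little or nothing to the evidence on the retained population.

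**Working it through.** **Inputs from the documents.** Power target 80% and overall type 1 error 2.5% (SAP 4.1); 1:1 allocation and 10% drop-out (protocol Study Outline); combination of stage-wise p-values by the Bauer and Köhne method (SAP 5.3). Planned and interim sample sizes, effect size and SD are redacted, so there is no stated figure to reproduce.

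**Assumptions.** The 2.5% is one-sided (the readable text does not say). The required total is an evaluable number, and the number enrolled exactly equals it. Drop-outs contribute nothing.

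**Step 1: power when a fraction r of the required patients is available.** This form needs no sample size:

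power = Φ(√r × (z₀.₉₇₅ + z₀.₈₀) − z₀.₉₇₅), with z₀.₉₇₅ = 1.960 and z₀.₈₀ = 0.842.

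At 10% drop-out, r = 0.90: Φ(0.9487 × 2.802 − 1.960) = Φ(0.698) = 0.757.

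| Drop-out | r | Power |
|---|---|---|
| 0% | 1.00 | 80.0% |
| 5% | 0.95 | 78.0% |
| 10% | 0.90 | 75.7% |
| 15% | 0.85 | 73.3% |
| 20% | 0.80 | 70.7% |

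If the 2.5% were two-sided, 10% drop-out would give 75.3%.

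**Step 2: the same loss under a two-stage test.** A simulated product-of-p-values test with equal stages and no early stopping, set to 80% power, gives 75.7% when 10% is lost in both stages. It gives 77.9% when 10% is lost in stage 2 only.

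**Step 3: the two rules side by side.** Assume an effect of 0.5 SD. The evaluable total is 4 × 2.802² / 0.5² = 125.6, so 126. Suppose 126 are enrolled when the re-estimation returns 126.

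- SAP 4.1: 126 is not more than 126, so stop.
- SAP 6.1 and protocol 4.3.3: expected evaluable = 126 × 0.90 = 113.4, below 126, so continue to 126 / 0.90 = 140 enrolled.

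At 0.4, 0.6 and 0.8 SD the evaluable and enrolled totals are 198 and 220, 88 and 98, and 50 and 56.

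**Step 4: how often it matters.** With the whole requirement on an evaluable basis, the rules disagree only when it lies between 90% and 100% of the number enrolled. Simulating the adaptive design without enrichment, the SAP 4.1 wording costs about 0.2 percentage points of overall power or less. The settings, all assumed, were a true effect of 0.5 or 0.7 SD, an interim at 40–60% of planned N, enrolment overrun of 10–20% of N, re-estimation to 80% at the observed effect, and a cap of 1.5–2.0 N.

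**Step 5: enrichment.** The loss depends on the overrun during the interim, the share of those children inside the retained subgroup, and whether stage 2 is tested in that subgroup alone. None of these can be read in the documents, so no figure is given.

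**The case against.** The strongest reply is that the rule may already be sound. SAP 4.1 refers to SAP section 6 for sample size details, and the details there and in SAP 5.1 and protocol 9.1 and 9.4 are redacted. The required total may be defined there as already inflated for drop-out, as the Study Outline does for its enrolled number, or as specific to the retained population. If it is inflated, SAP 4.1 compares like with like and there is no drop-out shortfall. SAP 6.1 also already gives a fuller rule that allows for adaptations. SAP 8.3 keeps drop-outs in the primary analysis by multiple imputation, which may recover information from earlier CY-BOCS visits. All of this stands, and it limits the size of the point. It does not remove the conflict: SAP 4.1 does not cite 6.1, and on an uninflated reading the two instruct differently.

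Two stronger readings are tempting and are not supported:

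- **A reader might infer that enrichment would leave the trial badly underpowered.** No readable text says that children outside the subgroup count towards the requirement, or that stage 2 is tested in the subgroup alone; SAP 7 and 8.2 put all randomized patients in the primary analysis. If the stop rule fires, there is no future enrolment left to restrict. The SAP also commits to updating itself (section 2) and amending the protocol's selection criteria (section 4.2) if the design is adapted.
- **A reader might infer that SAP 4.1 breaches a guaranteed protocol minimum.** The Study Outline's minimum is an estimate, protocol 4.1 allows the total to change, and protocol 3.3.1 allows the sample size to be adapted. This is an inconsistency within the protocol. Whether the planned number is a floor is the sponsor's choice and may be stated in redacted text.

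**Conclusion.** The readable documents hold two enrolment-stop rules with different counts, and they can give opposite instructions when enrolment is close to the requirement. The literal SAP 4.1 rule can then stop short of what the re-estimation calls for. In the exact boundary case with 10% drop-out, power is about 76% (about 78% if only stage 2 loses patients) instead of 80%. This rests on the required total being an evaluable number and on a one-sided 2.5% level. The loss of about four points is an upper bound for that case because of multiple imputation, and the average loss over plausible designs is a small fraction of a point. Under enrichment the gap in the wording is real, but its size cannot be determined. The point is worth acting on because the conflict is plain and alignment costs almost nothing, rather than because a large loss of power has been shown.

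**What to change.** Make SAP 4.1 follow SAP 6.1. Suggested wording: *Enrolment will be stopped only if the re-assessed requirement does not exceed the number of evaluable patients expected, in the population carried forward, from those already enrolled, applying the drop-out rate at the time (see Section 6.1).* State whether the requirement is an overall total or refers to the post-interim part only, since protocol 3.3.1 describes the latter.

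In the protocol, reconcile the Study Outline, where the total may only rise from a minimum, with section 4.1, where it may change in either direction. Say whether the initial planned number is a floor.

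The cost is SAP and protocol wording. In boundary cases enrolment may run slightly longer, but only up to the number the re-estimation already requires; choosing a floor could add more patients.
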